4 DEFINITIONS

Acceptability: the perception among men and healthcare workers that the adaptable RITE intervention is agreeable, palatable and satisfactory.

Appropriateness: the perceived fit of the adaptable RITE intervention to address the problem of low uptake of VMMC among men and healthcare workers.

Clinic escort: the act of escorting/accompanying a participant interested in VMMC from the STI clinic to the VMMC clinic to ensure linkage to care.

Contamination: a situation where the study population become exposed to more than one intervention component

Feasibility: the extent to which the adaptable RITE intervention will be successfully carried out at Bwaila STI clinic.

Intensified health education: consistent and setting-specific education on VMMC incorporated into the routine STI/HIV health education provided at Bwaila STI clinic.

Interference: a scenario where other stakeholders implement an intervention(s) aimed to scale-up the uptake of VMMC at the study sites which may affect attribution.

Seasonality: periodic variation in the uptake of VMMC with calendar time

SMS reminder tracing: the act of reminding participants with a VMMC appointment about their date of procedure through short messaging service.

Time-to-uptake: the number of days from the day a participant is offered VMMC to the day they undergo VMMC

Transport reimbursement: refunding money used for transportation to Bwaila district hospital for participants who undergo VMMC using standard Malawi government rates.

Uptake: the action of undergoing VMMC.

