done at the VMMC clinic and in the community through outreach clinics and mobile vans. Data such as demographics, referral source, date and outcome of VMMC are recorded in registers. We will use these registers to track men referred from the STI clinic who will undergo circumcision. Men attending the STI clinic may either be index cases (symptomatic) or sexual partners (symptomatic or asymptomatic). Men with symptomatic STIs will not undergo VMMC on the same day of their STI clinic visit until they complete treatment for their current STI.

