6.3 Sample Size Calculation and Justification

Data on the incidence of VMMC among men with STIs is unavailable. Based on routine data, the Bwaila STI clinic sees about 60 patients per day. Of these, 27 patients are men. Using the prevalence of circumcision from the MoH integrated HIV Program third quarter report of 28% among men with STI, we estimate that at least 19 uncircumcised men will visit the STI clinic per day and at least 380 uncircumcised men per month. Since the project implementation period is expected to be about 6 months, we expect that a minimum of 2280 uncircumcised men will be exposed to our intervention and observed for VMMC uptake.

We will offer all men who express interest in VMMC to participate in a survey. We anticipate between 5-15% of the men will decline participation in the survey. All (approximately 12) healthcare workers will be offered to take the surveys. All available experts (approximately 10) will be offered to take a survey.

Sample size for surveys

Based on the total sample size of 80 men indicated below, we calculated that 67 surveys are required for each intervention component to achieve 95% confidence level with 5% margin of error [38]. We will offer all men who express interest in VMMC to participate in a survey. We anticipate between 5-15% of the men will decline participation in the survey. All (approximately

12) healthcare workers will be offered to take the surveys. All available experts (approximately 10) will be offered to take a survey.

Data Analysis

Overall, we will use descriptive statistics such as mean, median and proportion to describe the demographic characteristics of the study population by implementation block. Demographic characteristics will include but not limited to age, marital status, educational status and socio-economic status. These characteristics will be compared with the SOC group using Student's T-test or Chi-squared test at $\alpha=0.05$ and 95% confidence interval, assuming normal distribution.

Objective 1: To compare uptake of voluntary medical male circumcision between the standard of care and the different combinations of the RITE intervention among men attending Bwaila STI clinic in Lilongwe Malawi

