6.5 Limitations and anticipated challenges

Contamination may be challenge in this implementation study however, we believe we have partly addressed this by using wash-out periods of one week between interventions. Selection bias may be a potential limitation if men with certain common characteristics enroll to a specific intervention block and affect the uptake of VMMC. Seasonality (circular trends) is a well-known confounding factor in VMMC research. Men in LMICs prefer to undergo circumcision in the cold season [39]. Our study will recruit participants during a period that will transition through the cold season however, we will monitor circular trends by measuring the prevalence of circumcision among men at Bwaila STI clinic. Interference in this study will be defined as a stakeholder implementing any intervention aimed to scale-up the uptake of VMMC at the study sites.

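### The seasonality monitor tracks circumcision prevalence, a lifetime stock, and is uninformative about a moderate seasonal change in VMMC uptake

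*Combined protocol and SAP*

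**What the plan says.** Section 4 (Definitions) has: "Seasonality: periodic variation in the uptake of VMMC with calendar time". Section 6.5 (Limitations and anticipated challenges) adds: "Seasonality (circular trends) is a well-known confounding factor in VMMC research". It also notes that men prefer the cold season for circumcision, and that "Our study will recruit participants during a period that will transition through the cold season". The planned response is one clause: "we will monitor circular trends by measuring the prevalence of circumcision among men at Bwaila STI clinic".

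Section 6.3 (Sample Size Calculation and Justification) shows what the plan means by prevalence: "Using the prevalence of circumcision from the MoH integrated HIV Program third quarter report of 28% among men with STI". That is the share of men already circumcised. The same section says separately that the incidence of VMMC in men with STIs is not known.

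Under Implementation (6.6.2), standard of care (SOC) is observed first and four blocks of about 3 to 4 weeks follow in fixed order, with full RITE last. Under Data Analysis, uptake in each block is compared with SOC by a t-test without a calendar-time term. The logistic and Cox models name no such term either. The text provided describes no other seasonality measure, and does not say how the prevalence series would be read or used.

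**The concern.** The quantity monitored is not the quantity that confounds. Seasonal confounding acts through the number of men who come for VMMC in a given week. Prevalence among STI attenders sums circumcisions over many years. Nationally, section 5.1 puts the larger part of that stock down to traditional circumcision (18% against 9% medical). A change in the weekly VMMC rate enters such a stock slowly and in diluted form.

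This matters because season and intervention move together by design. With one site, SOC first and the blocks in sequence, any calendar trend in demand is mixed into every block-versus-SOC difference. The plan's one safeguard should at least be able to warn of such a trend.

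**Working it through.** **1. Reproduce the plan's accrual.** Section 6.3 (Sample Size) states "Of these, 27 patients are men", out of about 60 patients a day. At 28% circumcised, 27 × (1 − 0.28) = 19.4 uncircumcised men a day, stated as 19. Then 19 × 20 = 380 a month and 380 × 6 = 2,280. This matches "at least 19 uncircumcised men will visit the STI clinic per day and at least 380 uncircumcised men per month" and the stated six-month total. The 20 clinic days a month are implied, not stated.

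**2. Precision of the monitor.** It uses all men, so n = 27 × 20 = 540 a month, which is also a 4-week block at five days a week.
- SE of one monthly prevalence: √(0.28 × 0.72 / 540) = 1.93 points, a 95% interval of about ±3.8 points.
- SE of a difference between two months: √2 × 1.93 = 2.73 points.
- Smallest rise from 28% detectable with 80% power between two such periods (two-sided 5%): about 8.0 points. For 3-week blocks of 405 men it is about 9.3 points.

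**3. How far season could move it.** The documents give no local rate. As an assumption, take the national 8% of the target population for 2008 to 2014 (section 5.1) as a proxy. Spread over 7 years it is 8/7 = 1.14 points a year. Section 5.1 also says Malawi adopted VMMC in 2012, so the alternative is 8/3 = 2.67 points a year. Extra prevalence from a k-fold demand lasting three months = (k − 1) × (annual rate / 12) × 3.

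| Demand for three months | 1.14 points/year | 2.67 points/year |
|---|---|---|
| Doubled | 0.29 point (0.10 SE) | 0.67 point (0.24 SE) |
| Ten-fold | 2.6 points (0.9 SE) | 6.0 points (2.2 SE) |

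SE here is the 2.73 points for a two-month difference.

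**4. Sensitivity.**
- *More patients.* Section 6.2 (Study setting) gives about 80 patients a day instead of 60. With the same share of men, 80 × 27/60 = 36 a day, or 720 a month. The SE of a difference falls to √2 × 1.67 = 2.37 points, and a doubling is 0.12 to 0.28 SE.
- *Pooling.* Two three-month halves of 1,620 men give √(2 × 0.28 × 0.72 / 1,620) = 1.58 points. A doubling is then at most 0.18 to 0.42 SE.
- *Longer surge.* At 2.7 points a year, tripled for all six months, prevalence gains 3 × 2.7/2 = 4.05 points. Power to see this between two periods of 540 men is about 31%.
- *Much higher local rate (assumed).* At 10 points a year, six months add 5 points, with about 43% power. Doubled, they add 10 points, with about 94% power.

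**5. The other reading of the monitor.** If prevalence were loose wording for uptake among STI attenders, the monitor would be the primary outcome, which RITE is meant to change. It could not then separate season from intervention.

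**The case against.** The strongest reply is that the size rests on a national proxy. That is right: the rate is an assumption, and the figures hold only over the range shown. The conclusion for a doubling survives both ends of the range. A statement that no surge could ever show would not: a ten-fold surge at the higher rate is 2.2 SE, and a very high local rate doubled for six months would usually be seen.

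A reader might also infer that the series will look flat, will be taken as proof of no season, and that a seasonal rise will then be credited to RITE. The documents do not support this chain. Monthly values would scatter by about ±4 points from sampling alone and would also shift with the mix of attenders, so a false trend is as possible as none. The plan gives no rule for reading the series. The direction of bias is open too. The cold season is never dated, and the study window is May to October in the Main Aim but April to September under Study population. If the season ended before the last block, full RITE against SOC could be biased towards no effect.

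Finally, the deeper weakness is the lack of a concurrent control: at one site with sequential blocks, block and calendar time are nearly collinear. A better monitor does not cure that. This stands and limits what the change can achieve.

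**Conclusion.** The point holds in a limited form. The plan names a confounder defined by uptake and monitors it with a lifetime stock. Under the assumed national growth of 1.1 to 2.7 points a year, a three-month doubling of demand moves the monitor by about 0.3 to 0.7 point, against an SE of about 2.7 points for a two-month difference. The monitor is therefore uninformative about a moderate seasonal change. It could register an extreme one. Bias in the block-versus-SOC differences could run either way, and this safeguard would not reveal it. The result assumes 20 clinic days a month and the national proxy. That no other seasonality measure is planned is true of the text provided, in which most appendices are not reproduced.

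**What to change.** In section 6.5 (Limitations), replace the prevalence monitor with weekly counts of VMMC procedures from the Bwaila VMMC clinic register, among men aged 18 or over whose recorded referral source is not the STI clinic. Run the series from the SOC phase to the end of follow-up. Add the same calendar weeks of the previous year if those registers are available and the permissions cover them. Report the series beside uptake by block, and state in advance that block-versus-SOC conclusions will be qualified if it shows a calendar trend.

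The source is already in the plan. Section 6.2 (Study setting) says: "Data such as demographics, referral source, date and outcome of VMMC are recorded in registers". Under Data Collection, staff extract from it daily. The cost is a paragraph of protocol text and an extra tabulation, plus any permission needed for previous-year data.

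Limits to state with it:
- The series reflects other men and any outreach campaigns, and cannot separate a campaign from season.
- The documents do not say whether the register covers outreach and mobile-van procedures.
- It would miss interference confined to the STI clinic.
- It informs interpretation but does not remove the confounding of block with calendar time.

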6.6 Proposed publications

1. Study designs paper with a description of how the intensified health education and RITE were developed and the implementation science research methodology
2. The impact of the RITE intervention on uptake of VMMC among men at Bwaila STI clinic in Lilongwe Malawi. This will include results on time-to-uptake of VMMC and factors affecting uptake of VMMC

3. The acceptability, appropriateness and feasibility of the RITE intervention for improve uptake of VMMC among men attending a STI clinic in Lilongwe Malawi

6.7 Timeline of proposed scope of work (Work Plan)

The timeline and scope of work have been detailed in Appendix 19.

6.8 Study Budget

This PhD will be funded by National Institute of Health; Fogarty Global Health Fellowship (FGHF) grant and the D43 training grant number; D43 TW01 0060-01 under the Malawi HIV Implementation Research Scientist Training Program (M-HIRST). Details are in Appendix 20.

7 APPENDIXES

7.1 Appendix 1: Schema of the Implementation Stages

Figure 1: Stages of Implementation of the RITE intervention
